#### **9.1.2 Outcome Measures-PK Component**

##### **9.1.2.1 Primary Outcome Measure**

- Steady state TFV-DP concentrations at Week 12.

##### **9.1.2.2 Secondary Outcome Measures**

- Steady state TFV-DP concentrations at Week 12.

#### **9.1.3 Randomization and Stratification-PK Component**

There is no randomization in this study. The enrollment will be stratified by:

- Group 1 (Antepartum women 14-24 weeks' gestation) vs. Group 2 (Postpartum women who delivered 6-12 weeks prior to enrollment)

#### **9.1.4 Sample Size and Accrual-PK Component**

An important objective of the PK Component is to determine the TFV-DP concentration corresponding to optimal adherence. We will estimate the 25th percentile of the TFV-DP distribution in each of the two groups. [Table 2](#) shows estimated 95% CIs around the 25th percentile based on the normal distribution assumption at various sample sizes. With a sample size of 15 per group, the bounds of the 95% confidence interval are the 12th and 43rd percentile.

**Table 2: 95% Confidence Intervals of Estimated 25th percentile of TFV-DP Steady State Concentration (Css)**

Sample Size per Group	95% Confidence Interval (percentile)
15	(12 th , 43 th )
20	(13 th , 41 th )
30	(15 th , 38 th )
50	(17 th , 35 th )
80	(18.5 th , 33 th )
100	(19 th , 32 th )

**Table 3** shows the precision of the estimate of minimum detectable difference in means for comparisons of mean TFV-DP steady state concentrations in DBS between the antepartum and postpartum group, given different sample sizes per group, alpha 0.05 using a two sample t-test. For example, with a sample size of 15 per group the half width of the 95% confidence interval around the difference in means is .75 of the standard deviation.

**Table 3: Precision of Estimated Differences in Mean Css in DBS: PK Component**

Sample Size per Group	Precision of estimated difference in mean Css (between AP and PP group)
20	271 (64% of SD*)
18	287 (68% of SD)
15 (protocol targeted)	316 (75% of SD)
12	358 (85% of SD)
10	397 (94% of SD)

\*SD=423 (DOT-DBS Study, CROI 2017)

### 9.1.5 Monitoring-PK Component

Reports summarizing data on accrual, missed weekly visits, missed PrEP doses, doses with inadequate source documentation of direct observation, number and adequacy of DBS specimens reaching the testing laboratory, mode of delivery, and safety and tolerability of FTC/TDF will be compiled by the Data Management Center (DMC) and reviewed and discussed by the CMC. Reports will be sent at least monthly. Adverse events will be monitored throughout the follow-up period. If the CMC identifies any potentially treatment-related toxicities, which may compromise participant safety, it will determine whether the study needs to be suspended or modified. Refer to [Section 9.3](#) for details on monitoring by the CMC and Safety Monitoring Committee (SMC).

### 9.1.6 Analysis-PK Component

Prior to conducting analyses for the PK Component, the CMC (to include a minimum of the Protocol Epidemiologist and/or Statistician and the Pharmacologist), will review the pattern of completeness of each maternal participant's TFV-DP concentration data to determine suitability for inclusion in the analysis. Weekly TFV-DP concentration levels in DBS will be plotted for each maternal participant. In each of the two groups (antepartum and postpartum groups), the distributions of steady state concentration (Css) defined as the TFV-DP concentration observed at Week 12 corresponding to 6-7 day/week adherence ("excellent adherence"), will be summarized. Estimates of median, IQR, mean, standard deviation, and 95% confidence intervals will be calculated for each of the two groups. Differences in mean Css between the antepartum and postpartum groups will be evaluated using two sample t tests.

Estimated concentrations corresponding to numbers of doses/week (or percentages of doses taken) in the antepartum and postpartum periods will be derived from the two measures above (antepartum Css and postpartum Css after 12 weeks of daily dosing), assuming dose proportionality (in cases that doses were missed). The drug threshold corresponding to “excellent adherence” will be defined as TFV-DP levels meeting or exceeding the 25th percentile of the distribution of TFV-DP concentrations at Week 12 of the PK Component. “Excellent adherence” is defined as the TFV-DP concentration corresponding to 6/7 doses per week on average, based on Cottrell et al who modeled that at least 6/7 doses per week is needed for adequate drug concentrations in women. The PK testing laboratory will provide sites with a drug level result and reference ranges as it relates to the categorized level of adherence to use during adherence counselling sessions (24). The reference ranges will include approximately three adherence categories, aligned with other similar studies in the field. For example, excellent adherence (equivalent to six to seven doses per week), good adherence with room for improvement (four to five doses per week), poor adherence (one to three doses per week), and not taking any doses (undetected TFV-DP levels).

If in the PK Component, TFV-DP variability at Week 12 appears high, this will be discussed among the CMC. For example, the team will decide if the threshold corresponding to adequate adherence should be set at the median or a different percentile instead of the 25th percentile.

In addition, antepartum and postpartum TFV-DP concentration thresholds corresponding to “excellent adherence” and the adherence categories for Weeks 4, 8 of the PrEP Comparison Component will be derived using the methods described above but from the distributions observed at Weeks 4 and 8 of the PK Component. For additional details on PK data analysis please refer to [Section 10.2](#).

### 9.1.7 Decision to open PrEP Comparison Component

The CMC will use the PK data (see [Section 9.1.6](#)) and monitoring reports (see [Section 9.1.5](#)) to come to a decision regarding whether PK Component data are sufficient to recommend opening the PrEP Comparison Component. The CMC will then convene to review the matrix and present the decision to the SMC whether or not to open enrollment to the PrEP Comparison Component according to [Table 4](#). The decision will be communicated to study staff by way of a notification which will include detail of the adherence target identified in the PK Component.

**Table 4: Criteria to open enrollment to the PrEP Comparison Component**

	Acceptable	Requires CMC review group discussion
Evaluable Maternal Participants	15 or more in each Group in the PK Component who meet the evaluability criteria set out in Section 9.1.1	14 or less in any Group in the PK Component who meet the evaluability criteria set out in Section 9.1.1
PK Assay	15 or more maternal participants in each Group in the PK Component with valid and complete TVF-DP concentration data	
Css	Distribution of steady state concentration data available	
Target Threshold	Defined for both Groups in the PK Component	Not defined or defined for only one Group in the PK Component

## 9.2 PrEP Comparison Component

Primary outcome measures listed below will be addressed in the study's primary Statistical Analysis Plan, which will define the content of the Primary Analysis Report. This report will form the basis for the primary study manuscript and results reporting to ClinicalTrials.gov. Outcomes of interest for additional objectives intended for subsequent publications are listed under "Other" and "Exploratory" Outcome Measures.

### 9.2.1 General Design Issues: PrEP Comparison Component

The IMPAACT 2009 PrEP Comparison Component is a prospective non-randomized open label study. The objectives are to 1) estimate and describe PrEP adherence during pregnancy and post-partum among HIV-uninfected adolescent and young adult women (aged 16-24 years) who initiate once-daily FTC/TDF in pregnancy and are followed through 26 weeks postpartum when offered adherence support through mobile technology and drug level-directed counseling 2) compare maternal and infant adverse events (including pregnancy outcomes) at delivery and Week 26 postpartum between women who initiate PrEP and women who decline PrEP over the observation period but receive HIV risk reduction and SMS interventions.

Two important design issues regarding the PrEP Comparison Component are as follows: 1) Assignment to each of the two cohorts is determined by maternal participant choice rather than by randomization. The team agreed that it would be unethical to deny women at high risk of acquiring HIV infection the opportunity to use PrEP, given the mounting evidence that PrEP use is an HIV prevention strategy with proven effectiveness. Due to the non-randomized design, potential confounders of the association between PrEP use and adverse pregnancy or safety outcomes may be distributed differently in the two groups, introducing bias. For example, HIV-uninfected women in serodiscordant relationships may be more willing to initiate PrEP and may also be at higher risk of adverse pregnancy outcomes than women with partners of known HIV-uninfected status. To address the first challenge, potential confounders at entry and follow up will be measured and adjusted for in multivariable models. An important limitation is that particularly for endpoints with low event rates, the small sample size will limit the number of confounders that can be included in multivariable models. 2) A second important design issue is that statistical power is limited for making conclusions regarding the safety of PrEP in pregnancy or postpartum. This study will yield estimates of the incidence and prevalence of selected safety outcomes in each of the two groups, with 95% confidence intervals for descriptive purposes. The study allows adequate power to detect large cohort differences, depending on the true background rate of the event.

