### 9.2.4 Sample Size and Accrual

The PrEP Comparison Component will enroll a total of 350 (233 in Cohort 1 and 117 in Cohort 2) women over a 12-month period. Women will be followed through 26 weeks postpartum. Expected duration of follow-up for a given maternal participant is between 7 and 12 months depending on the gestational age of the pregnancy at enrollment. The following sample size and power calculations assume a final analysis sample of 300 women (200 in Cohort 1 and 100 in Cohort 2). The primary reason for the 2:1 enrollment into the two cohorts was to balance the need for a “No PrEP” comparison group (to provide the background rates for safety outcome measures) with the need for a large enough PrEP group to examine outcomes that would be restricted to women in that group (Adherence). To achieve this sample size at the analysis phase, this study will enroll ~350 women to accommodate a decrease of ~15% due to maternal attrition.

**Table 8** shows the expected precision of a range of PrEP adherence estimates across different sample sizes in Cohort 1. For example, with a sample size of 200 women in Cohort 1, the width of the 95% confidence interval for an estimated adherence rate of 75% is 13%.

**Table 8: Precision (shown as 2-sided 95% confidence intervals) of different estimates of the proportion with good adherence (for illustration, defined as meeting or exceeding the threshold corresponding to protective drug levels of TFV-DP) at different sample sizes for Cohort 1.**

% Adherent	Sample Size in Cohort 1			
	150	200	250	300
50	42-58%	43-57%	44-56%	44-56%
60	52-68%	53-67%	54-66%	54-66%
65	57-73%	58-72%	59-71%	59-70%
70	62-77%	63-76%	64-76%	65-75%
75	67-82%	68-81%	69-80%	70-80%
80	73-82%	74-85%	75-85%	75-84%

**Table 9** below shows the precision of estimates of safety outcomes (e.g. preterm birth) expected with a range of event rates and a sample size of 200 women in Cohort 1 and 100 women in Cohort 2. It is expected that the rates of these outcomes will be low particularly since this is a young group of healthy HIV uninfected women. To that end, a range of AE rates with corresponding confidence intervals is included in the protocol.

**Table 9: 95% Confidence Intervals for different possible event rates of safety outcomes in Cohort 1 (n=200) and Cohort 2 (n=100)**

Event Rate	95% Confidence Interval	95% Confidence Interval
	Cohort 1 (n=200)	Cohort 2 (n=100)
0.5%	(0, 2.8)	(0, 3.6)
2.0%	(0.5, 5.0)	(0.2, 7.0)
4.0%	(1.7, 7.7)	(1.1, 9.9)

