10.0%	(6.2, 15.0)	(4.9, 17.6)
15.0%	(10.4, 20.7)	(8.6, 23.5)
20.0%	(14.7, 26.2)	(12.7, 29.2)
30.0%	(23.7, 36.9)	(21.2, 40.0)

The study allows adequate power to detect moderate cohort differences from 8.5% to 16%, depending on the true background rate of the event, as summarized below in **Table 10**. The table shows minimum detectable differences in safety outcomes between Cohort 1 and Cohort 2 which could be achieved with 80% power and alpha=0.05. For example, based on a sample size of 200 in Cohort 1, and assuming a 2:1 enrollment among women agreeing to and declining PrEP, differences of at least 13% will be detectable between the two cohorts in the proportion of maternal adverse events for events with a 10% background rate (10% in Cohort 2, 23% in Cohort 1).

**Table 10: Minimum detectable differences in safety outcomes based on evaluable sample size of 300 for Cohort 1(n=200) and Cohort 2 (n=100), 80% power, alpha=0.05**

% with event in Cohort 2 (N=100)	% with event in Cohort 1 (N=200)	Odds Ratio
2%	10.5%	5.8
5%	15.6%	3.5
10%	23%	2.67
15%	29%	2.36
20%	35%	2.19
25%	41%	2.10

To address primary objective 2.3.2, the mean bone mineral content of infants at birth and at age 26 weeks will be estimated and differences in mean bone mineral content between infants in Cohort 1 and Cohort 2 will be evaluated using two sample t tests. **Table 11** shows the statistical

power the study would have to detect a range of estimated differences in means. For example, with a sample size of 200 in Cohort 1 and 100 in Cohort 2 this study will be able to detect differences in mean bone mineral content of at least 0.35 SD with 80% power. Based on the SMARTT study in the U.S., assuming a standard deviation of 16.6 (77) this would be equivalent to a difference in means of 5.81g. Assuming a standard deviation of 14.9 found in the P1084s study (79) this would be equivalent to a difference in means of 5.22 g.

**Table 11: Estimated Power to Detect the Mean Differences in Infant Growth Outcomes Infant DXA, Whole Body Bone Mineral Content (BMC) (g) at Birth (Mean=63.8, SD=16.6)\*\***

Difference to be Detected	Effect Size (SD)	Power (based on sample sizes*)		
		N1=200 N2=100	N1=180 N2=90	N1=160 N2=80
4% (of 63.8)	2.55 (16.6)	24%	22%	20%
5%	3.19	35%	32%	29%
6%	3.83	47%	43%	39%
7%	4.47	59%	55%	50%
8%	5.10	71%	66%	61%
9%	5.74	80%	76%	71%
10%	6.38	88%	84%	80%
0.25*SD	4.15	53%	49%	44%
0.30*SD	4.98	68%	64%	59%
0.35*SD	5.81	81%	77%	72%
0.40*SD	6.64	90%	87%	83%
0.45*SD	7.47	96%	94%	91%

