### Descriptive summaries:

Entry demographic, pregnancy, pregnancy history, psychosocial, sexual behavior and partner characteristics of women in Cohort 1 and women in Cohort 2 will be summarized and compared using chi square tests (or Fishers exact test as appropriate) for discrete variables and t tests or Wilcoxon rank sum tests for continuous variables. Logistic regression models will be fit to identify predictors of PrEP initiation.

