Incidence rate ratio (among PrEP exposed vs. PrEP unexposed women) of cumulative adverse events up to 26 weeks postpartum	Incidence rate ratio of cumulative AEs up to the week-26 postpartum visit (among PrEP exposed vs. PrEP unexposed women) estimated based on Poisson distribution (with 95% Wald CI).

Supplemental Analyses:

- Analyses will be repeated stratified by time period (i.e., antepartum (AP) and postpartum (PP), and within AP stratified by gestational age category of enrollment).
- Rates of maternal adverse events in AP and PP periods will also be calculated and compared across levels of PrEP adherence (based on TFV-DP levels in dried blood spots). Models will be fit adjusting for potential confounders.

- To compare time to first adverse event in PrEP exposed vs. PrEP unexposed women, the hazard ratio (95% CI) will be estimated with Logrank test p-value from Cox proportional hazards regression on time to first AE with PrEP exposure as a time-varying covariate.

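### The PrEP-exposed versus unexposed safety models should adjust only for covariates recorded at or before PrEP start, not for values measured during follow-up

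*Protocol*

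**What the plan says.** Assignment to cohort is by the woman's choice. Protocol 9.2.1 accepts that this can confound the safety comparison, gives partner HIV status as its example, and states the remedy: "potential confounders at entry and follow up will be measured and adjusted for in multivariable models". It then concedes that, especially for endpoints with low event rates, "the small sample size will limit the number of confounders that can be included in multivariable models".

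Protocol 9.2.6 (Primary Objective 2.3.2) plans univariable and multivariable logistic regression for the composite adverse pregnancy outcome and for each of its four components. It plans Cox regression for maternal and infant adverse events, with confounder adjustment mentioned. Person-time in Cohort 1 starts when PrEP is initiated; SAP 6.3.2 starts it at study entry.

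SAP 6.3.3 repeats the logistic models as supplemental analyses, controlling for potential confounders. SAP 6.3.2 also says "Models will be fit adjusting for potential confounders", but in the item that compares event rates across adherence levels; 6.3.4 has the same item for infants. The main adverse event estimands are Poisson rate ratios with no covariates named, and infant growth is compared with t-tests or Wilcoxon tests. SAP section 4 defines a maternal baseline, but no safety model refers to it when covariates are mentioned.

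**The concern.** A confounder of the PrEP comparison has to precede PrEP. In Cohort 1 everything recorded after entry follows the start of exposure. Such a value may lie on a path from PrEP to the outcome, in which case adjusting for it removes part of the effect. It may instead share causes with the outcome, in which case adjusting for it can create an association. The direction of the resulting bias is not predictable.

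The confounder-adjusted models matter because the main adverse event and infant growth comparisons name no adjustment. If the protocol's rule is applied as written, the analyses meant to deal with self-selection could bring in a bias of their own. Each follow-up covariate also takes a place in the model that an entry confounder needs.

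**Working it through.** **1. Timing, section against section**

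- Protocol 9.2.1: covariates from entry and follow-up, for the PrEP safety comparison.
- Protocol 9.2.6 and SAP 6.3.2: Cohort 1 exposure starts at PrEP initiation or study entry. Every later Cohort 1 value is post-exposure.
- Protocol 2.4.2, with its analysis in 9.2.6: sexual risk behaviour and STI are compared as outcomes between the same two cohorts. They cannot also be assumed unaffected by cohort.
- Same analysis: STI incidence is adjusted for baseline confounders only. The primary safety objective has no such limit.
- Appendices IIA and IIB: after entry, scheduled STI tests fall at postpartum Week 26 or early discontinuation, so normally after the pregnancy outcome.
- Protocol 6.2.1.2: a woman who delivers before the Week 8 or 12 visit has those evaluations done at the delivery visit. A nominally antepartum value can then be recorded after the outcome, and whether this happens depends on length of gestation.

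**2. The plan's own sample size**

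Inputs (protocol 9.2.4): the calculations "assume a final analysis sample of 300 women (200 in Cohort 1 and 100 in Cohort 2"). Enrolment is about 350, "to accommodate a decrease of ~15% due to maternal attrition": 350 × 0.85 = 297.5, close to 300. Table 10 lists differences that "could be achieved with 80% power and alpha=0.05", with the worked example "10% in Cohort 2, 23% in Cohort 1".

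Check of that example, two-sided, pooled normal approximation (sidedness is not stated for Table 10):

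- Pooled proportion = (100 × 0.10 + 200 × 0.23) / 300 = 56/300 = 0.187
- SE under the null = √[0.187 × 0.813 × (1/100 + 1/200)] = 0.0477
- SE under the alternative = √[0.10 × 0.90/100 + 0.23 × 0.77/200] = 0.0423
- z = (0.13 − 1.96 × 0.0477) / 0.0423 = 0.86, so power is 80.6%

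The example is reproduced. The other rows give 77.8% to 79.6% from the rounded percentages, and all six give 79.3% to 80.1% from the printed odds ratios. These are two-group calculations without covariates.

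**3. Parameters that the outcome models can carry**

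Events = 300 × event rate. Parameters = events ÷ assumed events per parameter. The documents give no such rule, so a range is shown.

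| Event rate | Events in 300 | At 20 per parameter | At 10 | At 5 |
|---|---|---|---|---|
| 2% | 6 | 0.3 | 0.6 | 1.2 |
| 4% | 12 | 0.6 | 1.2 | 2.4 |
| 10% | 30 | 1.5 | 3 | 6 |
| 20% | 60 | 3 | 6 | 12 |
| 30% | 90 | 4.5 | 9 | 18 |

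PrEP (1), age group (1), trimester (1) and country (3) make 6 parameters. Four countries are assumed, as SAP 2.1.1 lists for the PK Component. Six parameters need 60 events at 10 per parameter (60/300 = 20%) or 30 at 5 per parameter (30/300 = 10%). At 10% to 20%, the enrolment factors and PrEP can take up the whole allowance.

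**The case against.** The sentence in protocol 9.2.1 is general design discussion. It names no follow-up covariate, and the protocol defers detail to the SAP, where the adjusted models are supplemental. All of that is correct, and it limits the consequence. It does not remove the point: the sentence states a rule, and the SAP gives neither a covariate list nor a time limit that would override it.

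Exposure in the SAP also changes over time, since Cohort 2 women can start PrEP at Step 2. A value recorded in follow-up but before the switch can be a genuine confounder for them. This stands and is built into the fix. Adherence is itself measured during follow-up, so follow-up confounders are also relevant to comparisons by adherence level. Those should be left alone.

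Three stronger readings are tempting, and the documents do not support them.

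- A reader might infer that the protocol describes a path from PrEP through behaviour, STI or the microbiome to adverse outcomes. Section 1.2 discusses behaviour without linking it to pregnancy or safety outcomes. It links dysbiosis to preterm birth, but 1.3.4 leaves open whether oral FTC/TDF alters the microbiome.
- A reader might infer that the outcome models cannot be supported at all. No expected event count is given, only illustrative rates from 0.5% to 30% in Table 9. At 20% to 30% a short covariate list fits, and the protocol already discloses the limit for rare endpoints.
- A reader might infer that a propensity score must replace the outcome models. The protocol plans a model of uptake ("Logistic regression models will be fit to identify predictors of PrEP initiation"), and a score limited by the 100 decliners could carry 100/20 to 100/5, that is 5 to 20 parameters. It would add no events, however, and a score fixed at entry does not match the SAP's time-varying exposure.

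**Conclusion.** The concern holds for the adjusted PrEP-exposed versus unexposed comparison: the pregnancy composite, its components, and any adjusted adverse event model. Applied as written, the protocol's rule permits conditioning on possible consequences of PrEP, and nothing in the SAP prevents it.

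The size of the bias cannot be calculated. Any figure would need an assumed PrEP effect and an assumed share of it passing through follow-up variables, and the documents give neither. The direction is also open, so it should not be described as a pull toward no effect.

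The cost in parameters can be shown. For endpoints at about 4% or less (12 or fewer events in 300), the data support at most 0.6 to 2.4 parameters at 20 to 5 events each, which leaves little or no room beyond PrEP itself. For a composite at 20% to 30%, the allowance at 10 events per parameter is 6 to 9. These figures rest on 300 evaluable women, a common event rate in both cohorts, and the events-per-parameter convention.

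The main rate ratios and infant growth tests, which name no covariates, are not affected. The analysis-approach entry for the SAP's third estimand is not legible in the copy read, so nothing is concluded about whether its main odds ratio is adjusted.

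**What to change.** In protocol 9.2.1 and 9.2.6 and in SAP 6.3.2 to 6.3.4, state that models comparing PrEP-exposed with unexposed adjust only for values recorded at or before PrEP start:

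- study entry, for Cohort 1 and for Cohort 2 women who never start;
- up to the Step Change, for exposed time in Cohort 2/Step 2.

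Say at or before explicitly. The SAP's baseline definition takes the measurement nearest to entry, which could fall after it.

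Give an ordered covariate list that puts entry confounders first, such as country, age group, trimester and partner HIV status. State that comparisons across adherence levels are not covered by this restriction.

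Optionally, add a baseline propensity score analysis as a sensitivity analysis for low-event outcomes, with a robust variance and a balance table.

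The cost is wording in two documents and modest programming. The four priority covariates are already collected by entry, so no new data are needed.

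The restriction gives up any adjustment of the exposed-versus-unexposed contrast for factors that change after PrEP start. If the team wants that, it needs a method designed for time-varying confounding, specified separately.
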